3 SALURATE STUDY SUMMARY

| Study Title | Validation of salivary uric acid remote self-monitoring for early prediction of | | | | |
|------------------------|---|--|--|--|--|
| | hypertensive disorders of pregnancy. | | | | |
| Short Title | The Salurate Study. | | | | |
| Objective | To clinically and logistically validate a novel remote self-monitoring screening system | | | | |
| | that uses the measurement of salivary uric acid to identify women who are at risk of | | | | |
| | developing hypertensive disorders of pregnancy (HDP) several weeks earlier than | | | | |
| | current methods. | | | | |
| Study design | A multi-center observational, analytical cohort study conducted over a period of 18 | | | | |
| | months with health economics evaluation. | | | | |
| | | | | | |
| | The Salurate Study is non-interventional; data collected will not result in any changes | | | | |
| | to the participants' care pathway. | | | | |
| Study | St. George's University Hospitals NHS Foundation Trust | | | | |
| Centres | Epsom and St. Helier University Hospitals NHS Trust | | | | |
| Sample size | n=4000 pregnant women | | | | |
| Eligibility | Inclusion criteria: Pregnant women from age 16, with a viable singleton pregnancy at | | | | |
| criteria (overview) | >12 weeks' gestation and able to provide informed consent. Full list section 8.1. | | | | |
| (overview) | | | | | |
| | Exclusion criteria: Physical incapacity, lack of access to a smartphone and/or the | | | | |
| | internet data at home, language or educational barriers that would cause an inability | | | | |
| • | to read the instructions for use (IFU) or use the App. Full list section 8.2. | | | | |
| Outcome | Primary Outcome: | | | | |
| ivieasules | a) Clinical diagnosis of HDP to include; gestational hypertension, pre-eclampsia, | | | | |
| | and chronic hypertension with superimposed pre-eclampsia | | | | |
| | Secondary outcomes: | | | | |
| | b) To assess whether Salurate could detect other important placentally- | | | | |
| | mediated adverse outcomes for the woman and baby including but not | | | | |
| | limited to fetal growth restriction (FGR) and gestational diabetes (GDM). | | | | |
| | c) To assess the cost effectiveness of routine Salurate testing compared to | | | | |
| | current care methods. | | | | |
| | d) To assess the degree of compliance of pregnant women to a self-sampling | | | | |
| | weekly test regimen. | | | | |
| | e) To assess the algorithm efficacy in a demographically diverse population. | | | | |
| | | | | | |

3.1 Study Schema

4 BACKGROUND AND RATIONALE

4.1 Hypertensive Disorders of Pregnancy

Hypertensive disorders of pregnancy (HDP) are serious medical conditions that affect approximately 10% of pregnancies worldwide [1]. HDP are classified into four types; gestational hypertension, chronic hypertension, pre-eclampsia, and chronic hypertension with superimposed pre-eclampsia. HDP are amongst the leading causes of maternal and fetal morbidity and mortality worldwide [2].

The worldwide incidence rate of HDP continues to increase. Changes in socioeconomic conditions in India, Asia, Africa, and South America has led to conception at an older age and increasing obesity rates [3]; these are both established risk factors for HDP.

Not only does HDP present a serious risk to mothers and babies during and immediately after birth, but as summarised by Giorgione et al., there is an established link between HDP and a propensity for women to develop cardiovascular diseases in the decades postpartum [4]. There is evidence to demonstrate that HDP can cause persistent left ventricular diastolic dysfunction and abnormal geometry, which may explain this predisposition to cardiovascular diseases (CVD) [5] [6]. Prior to developing CVD, women who have previously been diagnosed with HDP exhibit risk factors including chronic hypertension, diabetes, and dyslipidaemia [7].

Meads et al. reviewed 19,500 published reports of 27 candidate tests and concluded that none was clinically useful [8].

4.2 Salivary uric acid

Salurate is a novel monitoring device which detects elevated levels of Salivary uric acid (SUA) and identifies pregnant women at risk from developing HDP.

Using salivary biomarkers for disease detection and monitoring has potential implications for a variety of conditions [9]. Sampling is simple, non-invasive and does not require clinical involvement, making it ideal for remote monitoring. Two different studies demonstrated that elevated SUA in pregnant women correlates with an increased risk of developing complications associated with gestational hypertension such as pre-eclampsia [10].

The National Institute for Health Research (NICE) guidelines for monitoring the conditions associated with HDP are equivalent [11], yet also not particularly effective [12]. MIAT propose that a remote monitoring system to detect elevated SUA could predict which women are at risk from developing HDP more effectively than current protocols (blood pressure, proteinurea, fundal height).

4.3 Study Rationale

4.3.1 Significance of Hypertensive Disorders

HDP are major obstetric complications that pose significant risks to maternal and fetal health. These conditions are associated with severe maternal and fetal morbidity and are amongst the leading causes of maternal and perinatal death [13]. Early prediction and timely intervention are crucial to improving maternal and fetal outcomes and reducing the burden on healthcare systems.

4.3.2 Potential Benefits of Early Risk Assessment

The Salurate pregnancy monitoring system offers a novel and innovative approach to predicting HDP. By continuously monitoring various physiological parameters and utilising advanced algorithms, Salurate aims to provide early risk assessments for the development of these complications before the onset of clinical symptoms. Early identification could facilitate targeted interventions, personalised care plans, and

appropriate management strategies to mitigate the severity of complications and improve pregnancy outcomes.

4.3.3 Addressing Current Diagnostic Limitations

Traditional methods for diagnosing HDP rely on clinical signs and symptoms that may not become apparent until the disease has progressed significantly [11]. This delay in diagnosis can lead to missed opportunities for early interventions. Salurate's potential to provide predictive information before symptoms appear could fill a critical gap in current clinical approaches, allowing for proactive and timely management.

4.3.4 Potential to Improve Maternal and Fetal Outcomes

If the study demonstrates Salurate's predictive capabilities are reliable and accurate, its implementation could lead to improved maternal and fetal health outcomes. Early detection of high-risk pregnancies may enable healthcare providers to initiate appropriate interventions promptly, reducing the incidence and severity of HDP, and ultimately leading to improved maternal and neonatal health.

4.3.5 Advancements in Prenatal Care

The Salurate pregnancy monitoring system marks a significant stride forward in prenatal care, leveraging technological innovations to improve risk assessment throughout pregnancy. Salurate has the benefits of being convenient, simple, pain-free, and non-invasive. Serving as a remote monitoring tool, Salurate effectively minimises the burden of hospital visits for expectant mothers and fosters seamless communication between women and healthcare professionals. Undertaking this study will add to the expanding pool of evidence supporting the adoption of technology-driven healthcare solutions, especially in obstetrics. Early prediction of pregnancy complications remains crucial, and Salurate offers a promising approach to address this vital aspect of maternal well-being.

4.3.6 Clinical and Public Health Implications

The findings from this study have the potential to influence clinical practice and public health policies. If Salurate proves to be effective in predicting HDP, it could be integrated into routine prenatal care protocols, enabling healthcare providers to offer more personalised and proactive care to pregnant women.

5 AIMS AND OBJECTIVES

5.1 Study Aim

To assess the efficacy of the Salurate pregnancy remote self-monitoring system in predicting the onset of HDP. By comparing the Salurate system with traditional diagnostic methods, this study aims to determine the sensitivity, specificity, positive predictive value (PPV), and negative predictive value (NPV) of Salurate in identifying pregnant women. Additionally, the study aims to evaluate the time-to-diagnosis using the Salurate system in comparison to conventional diagnostic approaches.

5.2 Primary Objective

a) To test the hypothesis that the inclusion of the Salurate pregnancy remote self-monitoring system in a pregnant woman's care pathway would predict the subsequent development of HDP prior to is currently possible using traditional methods.

5.3 Secondary Objectives

- a) To assess whether Salurate could detect occurrence of other important placentally-mediated outcomes such as fetal growth restriction (FGR) spontaneous preterm birth (sPTB), stillbirth and GDM.
- b) To assess the cost effectiveness of Salurate testing compared to current care methods.
- c) To assess the degree of compliance of pregnant women to a self-sampling weekly Salurate test regimen.
- d) To assess the algorithm efficacy in a demographically diverse population.

Note: the current care methods to diagnose HDP involve assessing blood pressure, proteinuria (diagnosed via urinalysis/24 hour collection), blood test results and/ or PIGF levels.

6 Salurate System

Salurate is a non-invasive, home-use self-sampling system.

A weekly saliva sample is taken in the morning before eating, drinking, or brushing teeth. This sample is applied to a colorimetric test paper (test cartridge). An enzymatic reaction occurs, which producing a purple colour of varying intensities. The intensity of colour change is directly proportional to SUA concentration.

Figure 1. Uric acid linearity and colour intensity

A custom developed smartphone app, used in conjunction with a cloud server, receives the image from the smartphone app and extracts the relevant data. This data is combined with previous weeks' data and presented to the prediction algorithm.

The prediction algorithm is designed to detect patterns in the data that identify whether a hypertensive event is likely to occur in the pregnancy.

Figure 2. Salurate System Overview

6.1 Salurate System Components

The Salurate System is comprised of 6 key components.

1. The **Swab**: A pre-packaged, sterile swab commonly used for saliva collection. Single use, manufactured from a non-hazardous polyurethane foam.

Figure 3. Swab and packaging

2. **Test Cartridge**: A bespoke enzymatic uricase colorimetric test assay. The intensity of the purple colour formed is directly proportional to the concentration of uric acid in the saliva sample. The test paper is encapsulated into a single-use test cartridge.

Figure 4. Test Cartridge

- 3. **Salurate Box**: Contains all equipment required to take a sample. The top of the box includes a designated test cartridge area for the purposes of facilitating image capture. The box top is also labelled with the Study ID in alphanumeric and QR form, and includes a simple colour chart (RGB). The colour chart is used by the Salurate Server to:
 - Adjust for differing lighting conditions
 - Adjust for a wide range of camera phone hardware

Figure 5. Salurate Box

Figure 6. Salurate Box Test area

- 4. **Mobile Application:** 'The Salurate App' is a custom designed smartphone app that participants will install on their smartphone. It's main features;
 - Facilitates the photographing of the colorimetric test paper (test cartridge)
 - Guides the participant through the Sampling process
 - Transmits this image to the Salurate Secure Server in a secure way
 - Reminds the participant when to take their sample
 - Displays relevant notifications and updates to participants
 - Provides a source of information about the study

Figure 7. Salurate App; Login, Welcome and Start screens

- Salurate Secure Server: A cloud-based server system that utilises the AWS platform. It will be designed by MIAT, and subject to independent security testing at regular intervals. The Salurate Secure Servers' primary functions;
 - To receive images transmitted from the Salurate App
 - To identify and extract colorimetric data from these images, and to generate predictions based on this extracted data
 - To act as a database of test kits, storing information including (but not limited to);
 - o Anonymised participant ID number
 - Test kit batch information
 - Test kit Inventory and location
 - Information relating to recruitment centres and recruiters
 - To control and issue notifications to participants and recruiters
- 6. **Clinician Portal**: A means of viewing, updating, and extracting data from the Salurate Secure Server. Clinician Portal access is password controlled, with access permissions granted by the Sponsor. The primary functions;
 - To facilitate the registering of test kits during the recruitment process
 - The KIT ID is entered into the Portal, thereby informing the Salurate Server that this kit is activated. This creates an anonymous link between the participant, and data held by The Sponsor
 - To facilitate the control of inventory

- To allow low and high-level administrative access to data
 - Low level; Midwife access, Operations access. High level; Data controller

| 禁 1234 | 2 1 te | | Pictude An | crived 🤒 | Details | | |
|-------------|--------------------------|-------------------|--------------|--------------|----------------------------|----------------------------------|--|
| ituty ID | 20164 | Iniution | Secto Dipity | Poper Sepiry | Hudy C | 103-460-788 Bock | |
| 25-456-708 | New | 2 | | | Lought 1 | AGAT | |
| 120-455-799 | Nexa | + | 2 | ÷. | | | |
| 23-468-799 | Bulo-Assembly | x-tech | 100 | 7.0 | Swab | | Mowile |
| 123-456-799 | Subi-Asiembky | x-Tech | 8 | £. | Solido Espina | 01/01/2024 | Summer Aug |
| 28-458-798 | Stock | MIRT | 01/01/2024 | + | | | |
| 23-456-700 | Stock - Limited Lifespon | MM | 01/01/2022 | + | Test Poper | | User |
| 123-450-798 | Stock + Expired | MAT | 01/01/2020 | 10 | and a second | | printing transpire |
| 123-458-788 | Allocated | MMT | 01/01/2024 | 01/01/2024 | | | |
| 23-456-788 | Allocated | MAT | 01/01/2024 | 01/01/2034 | | | |
| 23-456-799 | Disponithed | saund to Midwife | 01/01/2024 | (0/01/2024 | h | | |
| 22-455-788 | Dispotofead | Issued to Midwife | 01/01/2024 | 01/01/2024 | 0 | | |
| 25-450-798 | Stock | itsued to Midwife | 01/01/2024 | 01/07/2024 | GENERATE N | EM 100 | IMPORT NEW STOCK |
| 129-456-798 | Stock | tobued to Midwife | 01/01/2024 | 01/01/2034 | Carlor to 10-2 hours | Burlin Ch. | In case of the develop the day Case is a local of the result result of the inverse of the second se |
| 125-496-780 | Stock | Issued to Midwife | 01/01/2024 | 01/01/2024 | - 30.Ms (serendy in pro | skactore | the same entries and in some of |
| 123-456-799 | mood | incured to User | 01/01/2024 | 04/04/2024 | | | (Company) and the second of the |
| 33-458-701 | tenued | Issued to User | 01/01/2024 | 01/01/2024 | ALLOCATI | ON DETAILS | DISPATCH KITS |
| 125-459-798 | instand | Issued to User | 01/01/2024 | 00/00/2024 | Conversion in Adventure of | and to off the suggest latitized | Approximately restants to the part of the second states |
| 123-455-788 | seved . | Issued to User | 01/01/2024 | 00/01/2024 | | | |

Figure 8. Clinician Portal; inventory information

6.2 Sampling Procedure Overview

Figure 9. Sampling process, overview

7 STUDY DESIGN AND SETTING

7.1 Trial Design

A multi-center observational, analytical cohort study conducted over a period of 18 months with health economics evaluation.

7.3 Identification Of Participants

Participants will be recruited by the clinical team as they present at a clinic for their routine first trimester scan at 10-14 of gestation. Recruitment and participation involve no additional appointments or travel for the woman, but could extend the duration of their clinic visit by up to 30 minutes.

The potential participant will be shown information about the Salurate Study, as well as introduced to the sampling kit. They will be advised that participation is entirely voluntary and that they may withdraw at any time. It will be made clear that inclusion in the study (or subsequent withdrawal) will not affect their usual care.

Potential participants will be advised that results will not be accessible to their clinical team, and that no additional clinical intervention will take place as a result of participation in the study.

The clinical team maintain the right to exclude potential participants if they consider the Study to potentially interfere with or compromise the delivery of care to the pregnant woman.

7.4 Side Effects / Participant Inconvenience

The Salurate Study does not involve pharmaceuticals, revealed test results, medical intervention, and there are no known side-effects linked to the collection of saliva.

The only procedure outside of standard antenatal practice is that once per week, on the same day, at the same time and before drinking, eating, exercise or teeth cleaning, the participant will take a saliva sample and test it on the disposable device.

Participation in the Study causes no risk of physical hurt, embarrassment, or pain to the participant.

Participation involves no manual handling, physical exercise, or physical activity from which there is a risk of accidents occurring.

7.5 Biobank

No research biobank is involved.

8 ELIGIBILITY

8.1 Inclusion Criteria

- 1. Women, 16 years old or over with a singleton pregnancy
- 2. Viable intrauterine pregnancy on the 10-14 week scan
- 3. High risk (\geq 1:100) of HDP as determined by the ASPRE [14] algorithm¹
- 4. Medium risk of HDP as defined by an ASPRE risk between 1:100 and 1:300
- 5. Able to provide informed consent
- 6. Gestation at enrolment <16 weeks

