10.2 Screening

Prior to the 10-14 week dating scan, the clinical team will have assessed the pregnant woman with regards to her risk of developing HDP. This risk category (Low/Medium/High) will be recorded on her clinical notes and will be used by the recruiting clinician to determine study inclusion.

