15 STATISTICAL CONSIDERATIONS

A cohort of 4,000 participant mothers would experience an estimated 460 events overall (PE/PIH/ IUGR) assuming a prevalence of 11.5%, and 100 cases of IUGR (the least prevalent of the conditions being studied), assuming a prevalence of 2.5%, based on observations from the Denmark study. This sized cohort would allow sensitivity of the Salurate algorithm to identify IUGR to be estimated with a 2-sided 95% confidence interval (CI) to within plus or minus 10% of the point estimate (if sensitivity was actually 50%, i.e. 95% CI 40% - 60%) and this would improve to a more precise confidence interval to within plus or minus 6% of the point estimate if the sensitivity proved to be around 90% (i.e. 95% CI 84% - 96%).

Additionally, a cohort of N=4,000 would allow sensitivity of the Salurate algorithm to identify any of the events of interest (prevalence 11.5%) to be estimated with greater precision, with a 2-sided 95% confidence interval to within plus or minus 5% of the point estimate (if sensitivity was actually 50%, i.e. 95% CI 45% - 55%) and this would improve to a more precise confidence interval to within plus or minus 3% of the point estimate if the sensitivity proved to be around 90% (i.e. 95% CI 87% - 93%). Specificity will be estimated to a much higher degree of precision because the majority of participants/babies in the cohort will not encounter adverse outcomes, and so they will comprise the much larger sample.

All analysis will be conducted by the study statistician Professor [name], using StataSE v16.1 statistical analysis software.

The Salurate study is quantitative research (numerical outcome). The quantitative data for this study will be analysed and reported according to the relevant reporting guidelines (STARD, BMJ. 2015;351:h5527. PMID: 26511519 and TRIPOD BMJ 2015; 350:g7594. PMID: 25569120).

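### Inclusion criteria 3 and 4 cannot both be met as listed; the workable reading limits the cohort to ASPRE risk 1:300 or higher, which the summary, the routine-testing objective and the 11.5% prevalence do not reflect

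*Protocol*

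**What the plan says.** Protocol 8.1 is a single numbered list of six inclusion criteria. Criterion 3 asks for high risk, 1:100 or more, "of HDP as determined by the ASPRE [14] algorithm". Criterion 4 reads "Medium risk of HDP as defined by an ASPRE risk between 1:100 and 1:300". The other four (age and singleton pregnancy, viability, consent, gestation) must plainly all hold, and nothing marks 3 and 4 as alternatives.

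Section 10.2 says that a Low/Medium/High category is already in the clinical notes and "will be used by the recruiting clinician to determine study inclusion". It does not say which categories qualify.

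The summary in Section 3 gives the population as "Inclusion criteria: Pregnant women from age 16, with a viable singleton pregnancy at" more than 12 weeks, with consent and no risk restriction. The row is marked as an overview and ends "Full list section 8.1". One of the summary's secondary outcomes is "To assess the cost effectiveness of routine Salurate testing compared to" current care.

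Section 15 states that 4,000 women "would experience an estimated 460 events overall (PE/PIH/ IUGR) assuming a prevalence of 11.5" per cent, a figure taken from a Danish study whose population is not described. Section 10.4 records the ASPRE value on the CRF as a risk of PE before 37 weeks.

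**The concern.** Eligibility decides who enters the cohort, and a wrong cohort cannot be repaired in the analysis. A recruiter who follows 8.1 literally has a rule that almost nobody meets. A recruiter who follows 10.2 has a rule that does not name the qualifying categories. Two sites could enrol different mixes of risk, each believing that it follows the protocol.

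The interpretation is also at stake. Sections 5.1 and 15 make PPV and NPV planned accuracy measures, and both depend on prevalence. If the cohort holds only women at raised ASPRE risk, these values and the economic model fed by them describe that group. They give no direct information on low-risk women, who would be tested if Salurate became routine.

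**Working it through.** **Step 1. Compare the two criteria.** Criterion 3 is risk ≥ 1/100 = 1.0%. Criterion 4 is risk from 1/300 = 0.33% to 1/100 = 1.0%.
- If both are required, only the single value 1:100 qualifies.
- If either suffices, the rule is risk ≥ 1:300. Women below 1:300, who by elimination form the low category of 10.2, are excluded.

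**Step 2. Set the sections side by side.**

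| Place | Risk restriction |
|---|---|
| Section 3, population | none stated; defers to 8.1 |
| Section 3, economic objective | routine testing |
| Section 5.3, same objective | the word routine is absent |
| Section 8.1 | high and medium, no 'or' |
| Section 10.2 | category decides; qualifying categories not named |
| Section 10.4 | ASPRE value is for PE before 37 weeks, not HDP |
| Section 15 | 11.5% (PE/PIH/IUGR), source population not described |

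**Step 3. Reproduce the plan's own figures.** Events = N × prevalence; 95% half-width for sensitivity = 1.96 × √[Se(1 − Se)/events].
- Any event: 4,000 × 0.115 = 460. Half-widths are 4.57 points (Se 50%) and 2.74 points (Se 90%), stated as 5 and 3.
- IUGR: 4,000 × 0.025 = 100. Half-widths are 9.80 and 5.88 points, stated as 10 and 6.

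All reproduce. The sample-size arithmetic is sound for the prevalences assumed.

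**Step 4. Effect of another prevalence on precision.** The protocol gives no event prevalence for women at 1:300 or higher, so the values other than 11.5% are assumptions.

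| Prevalence | Events in 4,000 | Half-width, Se 50% | Half-width, Se 90% |
|---|---|---|---|
| 11.5% | 460 | 4.57 | 2.74 |
| 20% | 800 | 3.46 | 2.08 |
| 30% | 1,200 | 2.83 | 1.70 |

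A higher prevalence narrows the interval for sensitivity.

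**Step 5. Effect on PPV and NPV.** PPV = Se·p/[Se·p + (1 − Sp)(1 − p)]; NPV = Sp(1 − p)/[Sp(1 − p) + (1 − Se)p]. Se 80% and Sp 90% are assumed, and held constant across prevalences.
- p = 11.5%: PPV = 0.092/(0.092 + 0.0885) = 51%; NPV = 0.7965/(0.7965 + 0.023) = 97.2%.
- p = 20%: PPV = 0.16/(0.16 + 0.08) = 67%; NPV = 0.72/(0.72 + 0.04) = 94.7%.
- p = 30%: PPV = 0.24/(0.24 + 0.07) = 77%; NPV = 0.63/(0.63 + 0.06) = 91.3%.

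**Step 6. Gestation (minor).** Section 3 says more than 12 weeks, 7.3 recruits at the 10-14 week scan, 8.1 requires less than 16 weeks at enrolment, and 10.5 allows up to and including 16. A woman at 11 weeks meets 8.1 but not the summary; a woman at 13 weeks meets every statement.

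**The case against.** The strongest reply is that the intent is clear. The categories in 10.2 are mutually exclusive, so criteria 3 and 4 can only be alternatives and the defect is a missing 'or'. That stands against any suggestion that recruitment would produce an empty cohort. It does not settle which categories qualify, because 10.2 does not say and the summary names no restriction.

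It can also be said that the summary is an overview that defers to 8.1. That is right: the mismatch is an omission, not a contradiction. It remains a large one, since it removes a whole risk category.

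The word routine appears only in the summary's version of the economic objective, and Section 16 speaks of screening patients at risk. Validating a test in raised-risk women is a legitimate design, and Appendix 2 records that the criteria were reviewed and updated, so the restriction may be deliberate. All of this stands. It supports leaving the choice of population to the sponsor, but not leaving that choice unstated.

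The PPV and NPV figures rest on assumed inputs. They show how far these measures can move with prevalence; they do not measure an error in the plan.

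**Conclusion.** This must be fixed before enrolment relies on 8.1. As listed, criteria 3 and 4 are mutually exclusive except at 1:100. The workable reading restricts the cohort to ASPRE risk 1:300 or higher, and Sections 3, 10.2 and 15 do not carry that restriction through. Under the assumptions in the working, PPV could differ by about 16 to 26 points (51% against 67% to 77%) between a cohort at 11.5% prevalence and an enriched one. The true size is unknown, because the protocol gives no prevalence for the restricted group.

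Three stronger readings are tempting and are not supported:
- **That enrichment contradicts the 11.5%.** The Danish population is not described. The figure lies near the roughly 10% for HDP in all pregnancies in Section 4.1, but the comparison is inexact because 11.5% includes IUGR. The figure is unjustified for a restricted cohort, not shown to be wrong.
- **That the sample size is too small.** A higher prevalence adds events and tightens the sensitivity interval.
- **That Salurate cannot be earlier than ASPRE because ASPRE has 100% sensitivity in this cohort.** ASPRE is not named as the timing comparator. Sections 4.2, 5.3 and 15 point to blood pressure, proteinuria, fundal height, blood tests, PlGF and standard NHS monitoring data. The 100% would also hold only at a 1:300 cut-off, not at the protocol's own high-risk cut-off of 1:100.

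**What to change.** Replace criteria 3 and 4 with one rule that names the qualifying ASPRE categories and the outcome to which the ASPRE risk refers, consistent with 10.4. Make Sections 3, 8.1 and 10.2 state the same rule. Then, according to the sponsor's choice:
- **Restricted to 1:300 or higher:** restate or justify the prevalence and expected events in Section 15 for that population, and limit PPV, NPV and cost-effectiveness claims, including the word routine in Section 3, to it.
- **All categories enrolled:** say so, and report accuracy by ASPRE stratum. Section 10.4 already collects the ASPRE value.

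Reconcile the gestation statements in Sections 3, 7.3, 8.1 and 10.5 in the same amendment.

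If the restriction is intended, the cost is amendment wording and a rechecked event count. If all categories are to be enrolled, the cost is larger, because that changes who may be recruited under 8.1 as it now stands.
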